10.3.3 Additional Events Reported

Additional events that require reporting

In addition to the above criteria, AEs meeting either of the below criteria, although not serious per ICH definition, are reportable to the Sponsor.

- Is a cancer
- Is associated with an overdose

10.3.4 Recording AE and SAE

AE and SAE recording

- When an AE/SAE occurs, it is the responsibility of the investigator to review all documentation (eg, hospital progress notes, laboratory, and diagnostics reports) related to the event.
- The investigator will record all relevant AE/SAE information on the AE CRFs/worksheets at each examination.

- It is not acceptable for the investigator to send photocopies of the participant's medical records to the Sponsor in lieu of completion of the AE CRF page.
- There may be instances when copies of medical records for certain cases are requested by the Sponsor. In this case, all participant identifiers, with the exception of the participant number, will be blinded on the copies of the medical records before submission to the Sponsor.
- The investigator will attempt to establish a diagnosis of the event based on signs, symptoms, and/or other clinical information. In such cases, the diagnosis (not the individual signs/symptoms) will be documented as the AE/SAE.

Assessment of intensity

- An event is defined as "serious" when it meets at least 1 of the predefined outcomes as described in the definition of an SAE, not when it is rated as severe.
- The investigator will make an assessment of intensity for each AE and SAE (and other reportable safety event) reported during the study and assign it to 1 of the following categories:
 - Mild: An event that is easily tolerated by the participant, causing minimal discomfort and not interfering with everyday activities (for pediatric studies, awareness of symptoms, but easily tolerated).
 - Moderate: An event that causes sufficient discomfort to interfere with normal everyday activities (for pediatric studies definitely acting like something is wrong).
 - Severe: An event that prevents normal everyday activities. An AE that is assessed as severe should not be confused with an SAE. Severe is a category utilized for rating the intensity of an event; and both AE and SAE can be assessed as severe (for pediatric studies, extremely distressed or unable to do usual activities).
- Injection site redness, swelling, or hard lump from the day of vaccination through Day 14 postvaccination will be evaluated by maximum size.

Assessment of causality

- Did the Sponsor's product cause the AE?
- The determination of the likelihood that the Sponsor's product caused the AE will be provided by an investigator who is a qualified physician. The investigator's signed/dated initials on the source document or worksheet that supports the causality noted on the AE form, ensures that a medically qualified assessment of causality was done. This initialed document must be retained for the required regulatory time frame. The criteria below are intended as reference guidelines to assist the investigator in assessing the likelihood of a relationship between the test product and the AE based upon the available information.

- **The following components are to be used to assess the relationship between the Sponsor's product and the AE;** the greater the correlation with the components and their respective elements (in number and/or intensity), the more likely the Sponsor's product caused the AE:
 - **Exposure:** Is there evidence that the participant was actually exposed to the Sponsor's product such as: reliable history, acceptable compliance assessment (diary, etc.), seroconversion or identification of vaccine virus in bodily specimen?
 - **Time Course:** Did the AE follow in a reasonable temporal sequence from administration of the Sponsor's product? Is the time of onset of the AE compatible with a vaccine-induced effect?
 - **Likely Cause:** Is the AE not reasonably explained by another etiology such as underlying disease, other drug(s)/vaccine(s), or other host or environmental factors?
 - **Rechallenge:** Was the participant re-exposed to the Sponsor's product in the study?
 - If yes, did the AE recur or worsen?
 - If yes, this is a positive rechallenge.
 - If no, this is a negative rechallenge.

(Note: This criterion is not applicable if: (1) the initial AE resulted in death or permanent disability, or (2) the study is a single-dose vaccine study; or (3) Sponsor's product(s) is/are used only 1 time.)

NOTE: IF A RECHALLENGE IS PLANNED FOR AN AE THAT WAS SERIOUS AND MAY HAVE BEEN CAUSED BY THE SPONSOR'S PRODUCT, OR IF RE-EXPOSURE TO THE SPONSOR'S PRODUCT POSES ADDITIONAL POTENTIAL SIGNIFICANT RISK TO THE PARTICIPANT THEN THE RECHALLENGE MUST BE APPROVED IN ADVANCE BY THE SPONSOR CLINICAL DIRECTOR, AND IF REQUIRED, THE IRB/IEC.

- **Consistency with study intervention profile:** Is the clinical/pathological presentation of the AE consistent with previous knowledge regarding the Sponsor's product or drug class pharmacology or toxicology?
- The assessment of relationship will be reported on the CRFs/worksheets by an investigator who is a qualified physician according to his/her best clinical judgment, including consideration of the above elements.
- Use the following scale of criteria as guidance (not all criteria must be present to be indicative of a Sponsor's product relationship).
 - Yes, there is a reasonable possibility of Sponsor's product relationship:

- There is evidence of exposure to the Sponsor's product. The temporal sequence of the AE onset relative to the administration of the Sponsor's product is reasonable. The AE is more likely explained by the Sponsor's product than by another cause.
 - No, there is not a reasonable possibility of Sponsor's product relationship:
 - Participant did not receive the Sponsor's product OR temporal sequence of the AE onset relative to administration of the Sponsor's product is not reasonable OR the AE is more likely explained by another cause than the Sponsor's product. (Also entered for a participant with overdose without an associated AE.)
- For each AE/SAE, the investigator must document in the medical notes that he/she has reviewed the AE/SAE and has provided an assessment of causality.
 - There may be situations in which an SAE has occurred and the investigator has minimal information to include in the initial report to the Sponsor. However, it is very important that the investigator always make an assessment of causality for every event before the initial transmission of the SAE data to the Sponsor.
 - The investigator may change his/her opinion of causality in light of follow-up information and send an SAE follow-up report with the updated causality assessment.
 - The causality assessment is 1 of the criteria used when determining regulatory reporting requirements.

Follow-up of AE and SAE

- The investigator is obligated to perform or arrange for the conduct of supplemental measurements and/or evaluations as medically indicated or as requested by Sponsor to elucidate the nature and/or causality of the AE or SAE as fully as possible. This may include additional laboratory tests or investigations, histopathological examinations, or consultation with other health care professionals.
- New or updated information will be recorded in the CRF.
- The investigator will submit any updated SAE data to the Sponsor within 24 hours of receipt of the information.

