6.3 Measures to Minimize Bias: Randomization and Blinding

6.3.1 Intervention Assignment

Intervention randomization will occur centrally using an IRT system. There are 2 study intervention arms. Participants will be assigned randomly in a 1:1 ratio to receive V114 or Prevenar 13™.

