8.1.9 Vaccination Report Card

The investigator or delegate will train the participant's legally acceptable representative (parent/guardian) in the use of the paper VRC as indicated in Section 1.3.

Body temperatures, injection-site reactions, vaccine-specific complaints, other complaints or illnesses, and concomitant medications or non-study vaccinations will be recorded on the VRC as described in Section 1.3 and Section 8.3.3. The investigator or delegate will review the data captured on the VRC with the participant's parent/guardian.

For the AEs outlined above, the investigator will use the information provided by the participant's parent/guardian on the VRC, and verbally at the time of VRC review, to apply the appropriate assessment of intensity as described in Appendix 3.

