9.4.2 Safety Endpoints

Safety and tolerability will be assessed by clinical review of all relevant parameters including AEs and postvaccination temperature measurements following any vaccination with V114 or Prevenar 13™.

The safety endpoints include:

- Proportion of participants with solicited injection-site AEs (swelling, redness/erythema, tenderness/pain, and hard lump/induration) from Day 1 through Day 14 following any vaccination with V114 or Prevenar 13™
- Proportion of participants with solicited systemic AEs (irritability, drowsiness/somnolence, hives or welts/urticaria, and appetite loss/decreased appetite) from Day 1 through Day 14 following any vaccination with V114 or Prevenar 13™
- Proportions of participants with the broad AE categories consisting of any AE and a vaccine-related AE from Day 1 through Day 14 following any vaccination with V114 or Prevenar 13™
- Proportions of participants with an SAE, a vaccine-related SAE, and discontinuation due to an AE, and death from Day 1 (day of Dose 1) through completion of study participation
- Participants body temperature measured from Day 1 (day of vaccination) through Day 7 following any vaccination with V114 or Prevenar 13™

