9.9.2 Sample Size and Power for Safety Analyses

The probability of observing at least 1 SAE in this study depends on the number of participants vaccinated and the underlying incidence of participants with an SAE in the study population. Calculations below assume that 100% of the randomized participants will be evaluable for safety analyses. There is an 80% chance of observing at least one SAE among 330 participants in each of the V114 group and Prevenar 13™ group if the underlying incidence of an SAE is approximately 0.49% (1 of every 206 participants receiving the vaccine). There is a 50% chance of observing at least one SAE among 330 participants in each of the V114 group and Prevenar 13™ group if the underlying incidence of an SAE is approximately 0.21% (1 of every 477 participants receiving the vaccine). If no SAEs are observed among 330 participants in each of the V114 group and Prevenar 13™ group, this study will provide 97.5% confidence that the underlying percentage of participants with an SAE is approximately <1.1% (one in every 90 participants).

Table 6 summarizes the percentage point differences between the 2 vaccination groups that could be detected with ~80% probability for a variety of hypothetical underlying incidences of an adverse event. These calculations assume 330 participants in each group and are based on a 2-sided 5% alpha level. The calculations are based on an asymptotic method proposed by Farrington and Manning [Farrington, C. P. 1990]; no multiplicity adjustments were made.

Table 6 Differences in Incidence of Adverse Events Between the 2 Vaccination Groups That Can be Detected With an ~80% Probability (Assuming 2-sided 5% Alpha Level With 330 Participants in Each Group)

Incidence of Adverse Event		Risk Difference
V114 (%) N=330	Prevenar 13™ (%) N=330	Percentage Points
2.6	0.1	2.5
6.4	2.0	4.4
10.9	5.0	5.9
17.5	10.0	7.5
23.6	15.0	8.6
29.4	20.0	9.4
40.4	30.0	10.4

Incidences presented here are hypothetical and do not represent actual adverse experiences in either group. Based on an asymptotic method proposed by Farrington and Manning [Farrington, C. P. 1990]

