### Tier 3 Events

Safety endpoints that are not Tier 1 or 2 events are considered Tier 3 events. Only point estimates by treatment group are provided for Tier 3 safety parameters.

Medical device incidents due to syringe, if any, will be listed.

Table 3 Analysis Strategy for Safety Parameters

Safety Tier	Safety Endpoint †	p-Value	95% CI for Between-Group Comparison	Descriptive Statistics
Tier 1	Injection-site redness/erythema (Days 1 to 14)	X	X	X
	Injection-site swelling (Days 1 to 14)			
	Injection-site tenderness/pain (Days 1 to 14)			
	Injection-site hard lump/induration (Days 1 to 14)			
	Irritability (Days 1 to 14)			
	Drowsiness/somnolence (Days 1 to 14)			
	Hives or welts/urticaria (Days 1 to 14)			
Tier 2	Appetite loss/decreased appetite (Days 1 to 14)		X	X
	Any AE †			
	Any Vaccine-related AE †			
	Any SAE †			
	Any Vaccine-related SAE †			
	Discontinuation due to AE †			
	Death †			
Tier 3	Maximum temperature measurements meeting cut points ( $\geq 37.5$ °C, $\geq 38.0$ °C, $\geq 39.0$ °C, $\geq 40.0$ °C; Days 1 to 7)			X
	Specific AEs by SOC and PT ‡ (incidence $\geq 4$ participants in at least one of the vaccination groups)			
Tier 3	Specific AEs by SOC and PT ‡ (incidence $< 4$ participants in all of the vaccination groups)			X

AE = adverse event; CI = confidence interval; PT = preferred term; SAE = serious adverse event; SOC = system organ class; X = results will be provided.  
† These endpoints are broad adverse event categories. For example, descriptive statistics for the safety endpoint of “Any AE” will provide the number and percentage of participants with at least one AE.  
‡ Includes only those endpoints not pre-specified as Tier 1 or not already pre-specified as Tier 2 endpoints.

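### Intensity grades and maximum reaction size are required data, but no planned between-group comparison uses them, so a shift towards severe non-serious or large local reactions would not show

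*Protocol*

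**What the plan says.** **What is collected.** Protocol 8.1.9 has the investigator use the parent's report card and the verbal review "to apply the appropriate assessment of intensity as described in Appendix 3". That appendix (10.3.4) asks for a mild, moderate or severe grade for each AE and adds: "Injection site redness, swelling, or hard lump from the day of vaccination through Day 14 postvaccination will be evaluated by maximum size". It sets no size categories.

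**What is analysed.** Protocol 9.4.2 and sSAP 3.4.2 define the solicited injection-site endpoint as "Proportion of participants with solicited injection-site AEs (swelling, redness/erythema, tenderness/pain, and hard lump/induration) from Day 1 through Day 14", after any vaccination. The systemic endpoint has the same form. Neither has a size or intensity threshold. Protocol 9.1 lists both as primary safety endpoints. Tier 1 (Protocol Table 4, sSAP Table 3) compares the same occurrences; in the sSAP the first row begins "Injection-site redness/erythema (Days 1 to 14".

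**What else is compared.** Tier 2 covers any AE, vaccine-related AEs, SAEs, vaccine-related SAEs, discontinuation due to an AE, death, four maximum-temperature cut points (37.5, 38.0, 39.0 and 40.0 °C), and specific AE terms seen in at least 4 participants in a group. A footnote removes the Tier 1 terms from that last row. Protocol 9.6.2 and sSAP 3.6.2 also promise further summaries of key safety parameters after each vaccination, without naming intensity or size.

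**The concern.** Objective 1 is the safety and tolerability of V114. A comparison that records only whether a reaction occurred gives a small patch of redness and a large one the same weight, and likewise mild and severe irritability. If V114 made reactions more severe without making them more common, the Tier 1 rows would show no difference.

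The other rows do not fill the space. Protocol 10.3.4 itself separates severe from serious, so a severe non-serious reaction is outside the SAE rows. The discontinuation row catches only reactions that end vaccination. The rows for specific terms leave out the solicited ones.

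Timing matters too. Because no size cut-off is written down, any chosen after unblinding could be suspected of being driven by the results.

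**Working it through.** **1. Where the data go.**

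| Required item | Between-group comparison planned |
|---|---|
| Occurrence of each solicited AE, any dose | Tier 1: p-value and 95% CI |
| Temperature, graded | Tier 2: four cut points, 95% CI |
| Reaction that is an SAE or causes discontinuation | Tier 2: 95% CI |
| Intensity of tenderness/pain and systemic solicited AEs | None named |
| Maximum size of redness, swelling, hard lump | None named |

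**2. The plan's own detectability figures.** Inputs from Protocol 9.9.2 (repeated in sSAP 3.9.2): Table 6 "summarizes the percentage point differences between the 2 vaccination groups that could be detected with ~80% probability"; "These calculations assume 330 participants in each group and are based on a 2-sided 5% alpha level"; "Calculations below assume that 100% of the randomized participants will be evaluable for safety analyses". Allocation from 6.3.1: "Participants will be assigned randomly in a 1:1 ratio to receive V114 or Prevenar 13™".

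With n per group and p̄ the mean of the two rates:

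- SE₀ = √[2p̄(1−p̄)/n]
- SE₁ = √[(p₁(1−p₁) + p₂(1−p₂))/n]
- power = Φ[(|p₁−p₂| − 1.96·SE₀)/SE₁]

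At a null difference of zero this equals the Farrington and Manning method that the plan cites. For 6.4% versus 2.0%, p̄ = 0.042, SE₀ = 0.01562 and SE₁ = 0.01552. Then (0.044 − 0.0306)/0.01552 = 0.863, and power is 80.6%.

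The seven rows of Table 6, in order, give 79.6, 80.6, 80.1, 80.0, 80.1, 80.1 and 80.0%. The table reproduces; its arithmetic is not in question.

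**3. What a direct comparison of severe reactions could detect (hypothetical rates, 330 per group).**

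| Comparator | V114 | Power |
|---|---|---|
| 2.0% | 6.4% | 80.6% |
| 5.0% | 10.9% | 80.1% |
| 1% | 4% | 69.5% |
| 5% | 10% | 68.5% |
| 2% | 5% | 55.5% |

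**4. What the any-grade comparison would show for the same change.**

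*Pure shift:* reactions that would have been mild become severe. Any-grade incidence is equal in both groups, so the Tier 1 comparison flags a difference only at about the 5% chance rate.

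*All extra severe cases are new reactors:* any-grade incidence rises by the same number of points. Assumed comparator any-grade incidence is 50% to 80%.

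| Any-grade, comparator | Power, +4.4 points | Power, +5.9 points |
|---|---|---|
| 50% | 20.3% | 32.9% |
| 60% | 21.3% | 34.8% |
| 70% | 24.2% | 40.0% |
| 80% | 31.4% | 52.2% |

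A direct comparison of severe reactions has about 80% power for both of these changes.

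**The case against.** The strongest reply is that nothing here is an error. Objective 1 concerns the proportion of participants with AEs, and the endpoints deliver that. The sentence on maximum size is a recording instruction that no other text contradicts. This stands: the point is an omission, and the remedy an improvement.

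Four stronger readings are tempting, and the documents support none of them.

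- **A reader might infer that a formal test is missing.** Protocol 9.6.2 and sSAP 3.6.2 call even the Tier 1 p-values and intervals descriptive, and 9.8 makes no multiplicity adjustment for safety. What is missing is a pre-specified estimate.
- **A reader might infer that severity is ignored altogether.** Fever has four graded cut points, and serious or discontinuing reactions have their own rows. Clinical review of the safety data and the by-dose summaries might also display intensity or size, although neither is promised. sSAP 3.5.2 defines the denominators for by-dose analyses, so results are not only pooled over doses.
- **A reader might infer that counting over four doses pushes incidence to a ceiling where the groups cannot differ.** Power for a risk difference is unchanged when each rate p is replaced by 1−p, so 93.6% versus 98.0% also has 80.6% power. The plan gives no per-dose rates either.
- **A reader might infer that parents grade the reactions and that size is already on the report card.** The investigator grades, using what parents supply. The report card contents in Protocol 8.3.3 name the injection-site reactions but not their size, and 10.3.4 does not say on which form size is recorded.

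**Conclusion.** The point holds in a limited form. Intensity and maximum size must be assessed, yet neither enters any pre-specified between-group comparison. The part left uncovered is severe non-serious solicited AEs other than graded fever, and large local reactions.

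The size can only be illustrated. For a hypothetical severe rate of 6.4% versus 2.0%, a direct comparison has 80.6% power. The any-grade comparison has 20% to 31% if every extra case is a new reactor on a 50% to 80% base, and about the chance rate if reactions only shift in grade. Table 6 labels its rates hypothetical and ties them to no grade, and the any-grade base is an assumption. These figures show what could go unseen, not how likely it is. Neither the immunogenicity hypotheses nor the sample size is affected.

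**What to change.** Before unblinding, add to Protocol 9.4.2 and sSAP 3.4.2, and to Tier 2 of Protocol Table 4 and sSAP Table 3:

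- (a) the proportion of participants with a severe solicited AE, for tenderness/pain and for each systemic term;
- (b) the proportion with maximum size of redness, swelling or hard lump above cut-offs that the sponsor fixes before unblinding.

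For each, give V114 minus Prevenar 13 after any dose with the unstratified Miettinen and Nurminen 95% CI already specified for Tier 2. Show the same categories in the by-dose summaries already planned. State where maximum size is recorded, and confirm that it is captured for each dose.

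The opening of Protocol section 9 allows non-confirmatory analyses to be changed through the sSAP before unblinding, and Objective 1 carries no hypothesis, so the sSAP is an available route. The cost is some wording, a few tables and a few more unadjusted descriptive intervals. Sample size and alpha do not change, and the assessments are ones the protocol already requires.

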10.3.5 Reporting of AEs, SAEs, and Other Reportable Safety Events to the Sponsor

AE, SAE, and other reportable safety event reporting to Sponsor via electronic data collection tool

- The primary mechanism for reporting to the Sponsor will be the EDC tool.
 - Electronic reporting procedures can be found in the EDC data entry guidelines (or equivalent).
 - If the electronic system is unavailable for more than 24 hours, then the site will use the paper AE Reporting form.
 - Reference Section 8.4.1 for reporting time requirements.
- The site will enter the SAE data into the electronic system as soon as it becomes available.
- After the study is completed at a given site, the EDC tool will be taken off-line to prevent the entry of new data or changes to existing data.
- If a site receives a report of a new SAE from a study participant or receives updated data on a previously reported SAE after the EDC tool has been taken off-line, then the site can report this information on a paper SAE form or by telephone (see next section).
- Contacts for SAE reporting can be found in the Investigator Study File Binder (or equivalent).

SAE reporting to the Sponsor via paper CRF

- If the EDC tool is not operational, facsimile transmission or secure e-mail of the SAE paper CRF is the preferred method to transmit this information to the Sponsor.
- In rare circumstances and in the absence of facsimile equipment, notification by telephone is acceptable with a copy of the SAE data collection tool sent by overnight mail or courier service.
- Initial notification via telephone does not replace the need for the investigator to complete and sign the SAE CRF pages within the designated reporting time frames.
- Contacts and instructions for SAE reporting and paper reporting procedures can be found in the Investigator Study File Binder (or equivalent).

10.4 Appendix 4: Combination Products: Medical Device Incident: Definitions, Recording and Follow-up

The recording and follow-up procedures described in the protocol apply to all medical devices as described below. For purposes of this section, medical devices in scope for device information collection include devices intended to be used by a study participant according to the study protocol, that are manufactured by the Sponsor or for the Sponsor by a third party, procured by the Sponsor for human use and/or combination products, regardless of investigational or marketed product.

